#### 5. SUBJECT ENROLMENT:

# 5.1 Recruitment and inclusion visit

Potential study subjects will be contacted by an invitation letter about the LOOP study with initial basic information about the study. If interested in participating in the study, potential study subjects are asked to contact one of the participating hospitals (typically the geographically closest) and an outpatient consultation is scheduled (inclusion visit).

At the inclusion visit the study subjects will be informed about the study by an investigator (or assigned designee), who will also look up the subject's medical records, and will interview the patient with a focus on previous medical history (diabetes, heart disease, hypertension, AF etc.) to assess study eligibility.

Blood pressure will be measured, and an ECG and blood sample is taken. Baseline variables including CHA2DS2-VASc and NYHA class score will be recorded. Individuals with AF on the ECG will be excluded from participating and these patients will be referred for relevant treatment. Subjects will be screened for previously unknown diabetes and hypertension. If these diseases are detected the patients will be referred for further tests or therapy. Individuals who wish to participate will sign informed consent documents, complete the QoL questionnaires and The Montreal Cognitive Assessment (MoCA) tests, and will be randomized to either implantation of ILR or standard care. Subjects must personally sign and date the consent form.

Patients may have additional study tests performed (T-wave alternans test, echocardiography, MRI etc.).

For the purpose of this trial the following definitions will apply:

# Registration

A subject has signed the informed consent form and has been assigned a subject identification number generated by the computer generating code (but not yet randomized)

# Randomization

A subject has been assigned to one of the two treatments and has been assigned a randomization number.

#### Enrolment

A subject is considered enrolled once the subject is randomized and the ILR implantation (or control) has been performed.

# 5.2 Subject Registration:

After the provision of informed consent each subject will be registered in a web-based electronic eCRF (eCRF), protected by encryption. A subject identification number will be assigned during registration, and will be used to identify a subject throughout the trial and must be used on all study documentations related to that subject. The subject identification number must remain constant throughout the entire trial; it must not be changed at any time.

All entries in the eCRF up to and including randomization are performed at the participating centre. Subsequent follow-up visits can be entered at the participating hospital where the patient is being followed. Subject initials and date of birth as well as other information will be required for registration, including for example subject initials and date of signed informed consent.

# 5.3 Screen Failures:

Registered subjects, who are ineligible for the study based on screening assessments will be considered screen failures and entered as such into the eCRF. The following information will be required:

- Subject identification number
- Date of birth
- Reason for failing screening
- Date of last screening assessment

# **5.4 Randomization and Treatment Assignment**

Subjects, who successfully complete the screening assessment, and meet the eligibility criteria, will be randomized into the study. A computer generated randomization scheme will be generated to assign subjects to treatment, and those who fulfil the eligibility criteria (section 4) will be randomized in a ratio

of 1:9 to receive an ILR or to be a control, respectively. The investigator (or assigned designee) will access the central computer and obtain an assignment code at the randomization visit. The following information at a minimum will be required for randomization:

- Subject identification number
- Date of birth
- Confirmation, that the subject meets the eligibility criteria

This information will be entered into the eCRF. Subject must be randomized within 30 days of being identified at the referral hospital.

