# Sample size:

In total 6,000 subjects will participate: 1,500 randomized to receive an ILR (ILR group) and 4,500 randomized to receive standard care (control group).

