#### 3. EXPERIMENTAL PLAN:

#### 3.1 Study Design:

This is a prospective randomized, open-label (unblinded), controlled, parallel group multi-center study performed in Denmark. Participants are recruited following identification from Danish registries as well as from outpatient clinics, and after hospitalizations. The study will recruit individuals residing in Region Zealand, Region of Southern Denmark or the Capital Region of Denmark. Potentially, the study region will be increased to cover other parts of Denmark. Participants are randomized to either receive an ILR (ILR group) or not receive one (control group). The randomization occurs at a ratio of 1:3 (ILR group vs. control group). The LOOP study will comply with the standards of the CONSORT Statement. 

After successfully completing all screening and baseline procedures, subjects will be randomized in a ratio of 1 to 3 to receive an ILR or usual control. The ILR will be programmed according to study recommendations (see section 6.2).

The study flow chart is given in Appendix A and the study endpoints are defined in section 10.2. A steering committee (SC) will oversee the conduct of the study. Composition and roles of this and other committees are described in section 10.7.

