# 3.3 Number of Study Subjects:

Participants in this clinical investigation shall be referred to as subjects or patients. Approximately 6,000 subjects will be randomized in a ratio of 1:3 to receive an ILR (ILR group) or continue standard care regimen (control group).

It is expected, that the randomization period will last for 2 years. The decline rate is estimated to be <10 %. The cross over from control to the ILR group is expected to be <10 %, since an ILR implant is generally assumed to require a syncope or definite clinical suspicion of arrhythmia or a wish to quantify arrhythmia burden. Subjects discontinuing from the study prematurely will remain in endpoint follow-up unless consent is withdrawn. Statistical considerations are provided in section 10.3.

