# 10. STATISTICAL CONSIDERATIONS:

# 10.1 Study Design:

This is a prospective randomized, open-label (unblinded), controlled, parallel group multi-center study performed in Denmark. Patients are recruited following identification from Danish registries as well as from outpatient clinics, and after hospitalizations. The study will recruit individuals who live in the Capital Region of Denmark, Region Zealand or the Southern Region of Denmark. The study is expected to conclude when 279 strokes have occurred or 6,000 study subjects have been followed for at least 36 months, which is expected to be approximately 5 years after enrolment of the first subject. Subjects meeting the eligibility criteria will be randomized to either receive an ILR (ILR group) or not ie, continue standard care (control group). The randomization occurs at a ratio of 1:3 (ILR group vs.

control group) as described in section 5.2. The LOOP study will comply with the standards of the CONSORT Statement. The study design is further described in section 3.

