#### 10.3 Sample Size Considerations:

We expect that 30% of the participants will have documented AF episodes lasting ≥6 minutes (and per protocol qualifying for OAC) during ILR monitoring for at least three years. The study population is expected to have a stroke rate of 0.7%/year in non-AF patients, and 2%/year in AF patients not treated with OAC. While we expect the number of AF-related strokes to be reduced by OAC, we assume that strokes unrelated to AF will not be influenced by this. We also include the assumption that 3% of all participants in the control group will become diagnosed with AF and start OAC. The annual rate of the primary end point in the control group is thus expected to be 1%. Finally, we expect that 5% in the ILR group will not be monitored due to refusal of ILR implantation or ILR explantation due to discomfort. These patients will participate at the same risk as patients in the control group and will be included in the analysis of the primary endpoint according to the intention-to-treat principle. We thus expect the overall hazard ratio to be 0.65. To analyse this reduction in the primary endpoint with a 2-sided α-level of 0.05 and a power of 80% in a 1:3 intervention:control-randomized population, we will need 279 primary events. Follow-up duration will be adjusted to accommodate the number of primary events. With an assumed length of inclusion period of 1-2 years and a median follow-up up 4 years, 6000 subjects will be needed.

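### Section 5.4 sets ILR-to-control allocation at 1:9, while the rest of the protocol is built on 1:3; at 279 events, 1:9 would cut power from about 80% to about 44–47%

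*Protocol*

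**What the plan says.** Section 5.4 (Randomization and Treatment Assignment) says that a computer-generated scheme will assign subjects and gives the ratio as "of 1:9 to receive an ILR or to be a control, respectively". It is the only section that describes how the scheme is generated and how an investigator obtains an assignment.

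Every other statement on allocation is 1:3:

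- Section 3.1: "The randomization occurs at a ratio of 1:3 (ILR group vs. control group"; the ratio is repeated in that section's second paragraph.
- Section 3.3: about 6,000 subjects at 1:3.
- Section 10.1: 1:3, with a pointer to section 5.2.
- Section 10.3: "a power of 80% in a 1:3 intervention:control-randomized population, we will need 279 primary events".
- Synopsis, sample size: "1,500 randomized to receive an ILR (ILR group) and 4,500 randomized to receive standard care (control group".
- Appendix G: 600 recorders purchased and a further 900 donated, 1,500 in total.

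Section 5.2 deals with subject registration and contains no allocation ratio.

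**The concern.** Whoever programs or audits the randomisation will turn to section 5.4, and there the number disagrees with the design. The cross-reference in section 10.1 does not settle the matter, because it leads to a section without a ratio. The section it should cite, 5.4, has the wrong ratio.

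The event target of 279 was derived for 1:3. Power for a given number of events depends strongly on how those events divide between arms, so a list at 1:9 would invalidate that target. Event-driven follow-up would not rescue the trial, because it stops at the count worked out for 1:3.

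**Working it through.** **Inputs, all from protocol section 10.3 unless noted:** hazard ratio (HR) 0.65; two-sided α 0.05; power 80%; 279 events; control rate 1% per year; 6,000 subjects; allocation 1:3 (section 10.3) or 1:9 (section 5.4). (z₀.₉₇₅ + z₀.₈₀)² = (1.960 + 0.842)² = 7.849. Competing deaths are ignored and hazards are taken as proportional.

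**Arm sizes.** 1:3 gives 6,000 × 0.25 = 1,500 ILR and 4,500 control, matching the synopsis and the 600 + 900 devices. 1:9 gives 6,000 × 0.10 = 600 and 5,400, leaving 900 of the 1,500 funded devices unused.

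**Reproducing 279 at 1:3.** Freedman's formula with k = ILR/control:

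E = 7.849 × (1 + k·HR)² / [k(1 − HR)²]

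- k = 1/3: 7.849 × 1.2167² / (0.3333 × 0.1225) = 285 events, within 3% of 279.
- Power at 279 events: Φ[√(279/3) × 0.35/1.2167 − 1.96] = Φ(0.814) = 79.2%.

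Schoenfeld's formula, E = 7.849 / [p(1 − p)(ln HR)²] with p the ILR share, gives 7.849/(0.1875 × 0.1856) = 226 events at 1:3, and 87.6% power at 279. It does not reproduce the protocol's figure, so Freedman is taken as the basis.

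**The same calculation at 1:9 (k = 1/9).**

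- Power at 279 events: Φ[√(279/9) × 0.35/1.0722 − 1.96] = Φ(−0.143) = 44.3%.
- Events for 80% power: 7.849 × 1.0722² / (0.1111 × 0.1225) = 663.

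**Why the loss is so large.** Under HR 0.65 the ILR share of events is 0.25 × 0.65/(0.25 × 0.65 + 0.75) = 17.8% at 1:3, or about 50 of 279. At 1:9 it is 0.10 × 0.65/(0.10 × 0.65 + 0.90) = 6.7%, or about 19 of 279.

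**Cross-checks.** The simulation used exponential event times, 6,000 subjects and stopping at the 279th event, with 20,000 trials per ratio. The binomial calculation conditions on 279 events.

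| Method, 279 events, HR 0.65 | 1:3 | 1:9 |
|---|---|---|
| Freedman | 79.2% | 44.3% |
| Log-rank simulation | 81.6% | 47.3% |
| Exact binomial on the event split | 82% | 39% (Wald) to 49% (score, likelihood ratio) |
| Schoenfeld | 87.6% | 57.9% |

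**If calendar time were fixed instead.** The follow-up that yields 279 events at 1:3 (about 5.2 years per subject) would yield about 295 at 1:9, with 46% power by Freedman. At 4 years, 1:9 yields about 227 events and 37%.

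**The case against.** The intended ratio is hardly in doubt: the explicit statements elsewhere, the arm sizes, the event calculation and the device budget all agree on 1:3. Section 5.4 is also not the only prescriptive text, since sections 3.1, 3.3 and 10.1 say how subjects will be randomised. The 1:9 figure may be left over from an earlier plan: a tenth of 6,000 is 600, the number of devices first purchased in Appendix G. That is inference, and nothing shows that a list was ever generated at 1:9, so the power loss is conditional. The size also depends on the formula, because Schoenfeld leaves 58% at 1:9. Finally, the ratio does not affect the validity of the intention-to-treat set or of the planned cumulative-incidence and Cox analyses, which work at any allocation.

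Most of this stands as qualification. The ratio bears on the event target and power, not on the validity of the analysis, and the loss is a risk rather than a demonstrated fact. The Schoenfeld figure carries less weight because that formula gives 226 events at 1:3, not 279, and even there the drop is about 30 points (87.6% to 57.9%). None of it removes the contradiction. If 1:9 is a remnant of a real earlier plan, that is a further reason to check the list.

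**Conclusion.** The point holds. The protocol contradicts itself on the allocation ratio, in the section that governs how the randomisation scheme is built, and its cross-reference does not resolve the conflict. This must be corrected whether or not any list followed section 5.4.

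If a list did follow it, power at 279 events would be about 44% (Freedman) to 47% (simulation) instead of the stated 80%, and roughly 663 events would be needed in place of 279 (470 by Schoenfeld). These figures rest on HR 0.65, 6,000 subjects, proportional hazards and no competing deaths. The statement that power falls below 50% belongs to the Freedman, simulation and exact calculations, and not to Schoenfeld.

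**What to change.** 1. Change the ratio in section 5.4 to 1:3 (ILR to control).
2. Correct the cross-reference in section 10.1 from 5.2 to 5.4.
3. Confirm in writing, from the randomisation system itself, that the live list was generated at 1:3 throughout.
4. Only if some subjects were allocated at 1:9: report the dates and numbers, and stratify the primary comparison by allocation period. The chance of receiving an ILR would then have changed over calendar time, and an unstratified comparison could be confounded by it.

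Steps 1 to 3 cost a one-line amendment, a corrected reference and one check of the list. They change neither the sample size nor the event target.

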# 5.5 Re-Screening:

Registered subjects, who do not meet all eligibility criteria on the first screening occasion may be rescreened for the study at a later time. Such subjects may begin screening procedures again two weeks after the date of the last screening assessment. Rescreened subjects will retain the originally assigned subject identification number: However, the rescreening attempt will need to be entered into the registration computer.

#### **6. TREATMENT PROCEDURES:**

Implantation of a Loop Recorder (ILR) will be performed according to local standards and within four weeks of randomization.

#### 6.1 ILR device:

Devices from Medtronic (Reveal LINQ or newer comparable devices) with capability for remote monitoring will be used in this trial. Information on specific ILR data can be found in Appendix F.

# 6.2 ILR procedures:

#### 6.2.1 Preparations and setting:

Preoperative biochemical parameters as required by local guidelines (which may include variables such as INR, blood cells, creatinine, sodium, potassium).

The device is implanted at the hospital using standard sterile technique; not necessarily in an operation or cardiac catheterization facility. An intravenous injection line (such as Venflon) is optional, but is inserted if i.v. antibiotics are given.

#### **6.2.2 Medication in relation to surgery:**

Antibiotics are given according to study guidelines. It is suggested to give at least one dose of i.v. cefuroxime (Zinacef) 1.5 g or dicloxacillin (Diclocil) 0.5-1.0 g immediately prior to the procedure, or oral dicloxacilling (Dicillin) 0.5-1.0 g at least one hour prior to the procedure. It is optional to give additional antibiotics. In case of allergy to penicillin alternative antibiotics is recommended according to local

guidelines. Sedatives are not recommended. Local anaesthesia is given according to each centre's local guidelines.

# 6.2.3 The surgical procedure:

The ILR is positioned subcutaneously on the left side of the chest using supplied incision and insertion tools. Measurement of the device orientation is optional. Securing optimal electrocardiogram before wound closure is recommended. At each centre, the implantation of the ILR is performed by either a senior cardiologist or a medical doctor under general supervision of the local senior cardiologist.

# 6.2.4 Loop Recorder programming:

The ILRs should be programmed according to study guidelines, and details are specified in Appendix E.

# 6.2.5 Post operative monitoring:

After the implantation, one hour of observation at the facility is recommended, and after this the patient can be discharged from hospital. The patients will receive advice with respect to skin inspection in the surgical region, treatment of local pain after surgery.

# 6.2.6 Remote follow-up:

Study participants will be instructed in the automated daily remote transmissions which require bedside setup of the MyCareLink Patient Monitor at their home along with patient-initiated transmissions to transfer extra data.

#### 6.3 Concomitant Therapy:

Throughout the study investigators may prescribe any concomitant medications or treatments necessary to provide adequate supportive care. Information on concomitant therapy will be collected on the appropriate case report form.

If the ILR monitoring detects severe bradycardia, ventricular tachyarrhythmia or other arrhythmia these will be dealt with according to clinical guidelines. For study guidelines how to treat AF, see section 7.7. It is possible for the patient to participate in another trial, both including devices (such as stents) or medical therapy.

#### 6.4 Prescribed therapy during the study period:

All subjects (both ILR group and control patients) should receive optimal medical therapy for their inclusion criteria disease (hypertension, diabetes, heart failure or stroke). The national guidelines for treatment of heart failure and hypertension are described in the guidelines from the Danish Society of Cardiology which can be downloaded from the web page www.cardio.dk. The standard regimen for stroke patients is described in the Danish Reference Programme 2013 (Dansk Apoplexi Selskab).

#### 7. STUDY PROCEDURES:

A tabular schedule of study procedures is given in Appendix A. Written informed consent must be obtained before performing screening procedures. The investigator is responsible for ensuring that all assessments are performed according to the protocol and that the appropriate data are recorded in the eCRFs. Missed visits, test(s), that are not done and examinations, that are not conducted, must be reported on the eCRFs.

# 7.1 Subject Screening:

During screening each subject will be evaluated for inclusion in the study. All laboratory assessments scheduled for screening will be done by the local laboratory. The following procedures, screening evaluations and assessments will be done once within 21 days prior to randomization:

- Obtaining or verifying informed consent
- Medical history, including previous, surgical procedures
- NYHA functional classification: The severity of heart failure will be evaluated by the investigator or the designee at the respective study visits. If possible a subject should be evaluated by the same person throughout the study.
- CHADS-VASc score
- Physical examination, including height, body weight
- Ongoing medical therapy
- Blood samples for routine biochemical testing, plasma troponines, p-BNP and for storage in the study related research biobank. After analysis of the material from the study related research biobank surplus biological material is transferred to a biobank for future research.
- 12-lead ECG

If laboratory samples are missing, destroyed, unable to be analysed or results are considered and documented by the investigator as being obviously incorrect, a subject may be re-tested.

# 7.2 Follow-up Phase:

# 7.2.1. The main study:

The ILR devices will be implanted over the course of 12-24 months (1-8 implantations per week in each of the centres), starting at the beginning of 2014.

• Participants in the ILR group will be seen at in-hospital visits at 12, 24 and 36 months after ILR implantation. Between in-hospital visits they will be followed by daily automatic ILR remote telemedicine transmissions. Data from the ILRs are automatically transmitted to a central database. Every day, an experienced medical doctor reviews the recent transmissions in the database. Subjects will be contacted if transmissions are not received in a period of 14 days, and any system malfunctions will be corrected. If a new-onset AF episode lasting minimum 6

minutes is detected, two senior cardiologists independently evaluate the transmission. In case of disagreement, a third senior cardiologist will independently evaluate the episode. If the two or two of three cardiologists confirm the diagnosis of AF, OAC will be initiated by the local center (see section 7.8), and this will be registered in the eCRF. Remote monitoring will continue until the end of battery life, study withdrawal, or death occurs. At in-hospital visits, QoL and MoCA forms will be filled. Adverse events will be collected at study visits and by lookup in medical records and registries at least on a yearly basis until the end of study.

Participants in the control group will be seen only at inclusion and after the 3 year follow-up.
 During this period they will be seen by their general practitioner. Between the scheduled visits
 QoL forms will be sent by mail. MoCA forms will be filled in on the final follow-up. Adverse events will be collected at study visits and by lookup in medical records and registries at least on a yearly basis until the end of study.

Additional visits are made at the discretion of the caring physician. Throughout the study the investigator or study nurse/coordinator should continue to provide appropriate medical care.

The following assessments and procedures will be performed at specified time points during the study and will be recorded in the eCRFs (for details please see Appendix A, section a and b):

- CHADS-VASc score: At randomization.
- Blood sample: At randomization. Some participants might have additional blood samples taken.
- NYHA functional classifications: At randomization and (12, 24,) 36months.
- Assessment of QoL and cognitive function: At randomization, months 12, 24 and 36.
- Vital signs (BP, HR ...): At randomization and at (12, 24), 36 months.
- 12-lead ECG: At randomization and at (12, 24), 36 months.
- Concomitant therapy: At randomization and months 12, 24, 36 and by lookup in medical records and registries at least on a yearly basis.
- Remote Loop Recorder readings: Daily
- Adverse events (AEs): At clinical visits and by lookup in medical records and registries at least on a yearly basis (see section 9 for definitions).

Information on all AEs, that occur from study day 1 after randomization will be recorded in the appropriate eCRFs on study visits and by lookup in medical records and registries at least on a yearly basis. All serious adverse events (SAEs) will be reported to the study office within one working day of discovery (see appendix C), and a SAE form must be completed (see section 9.3 for definitions). Bleeding complications will be registered according to the suggestions by the International Society for Thrombosis and Haemostasis (Schulman and Kearon, 2005). For the efficacy analysis of mortality, the endpoint committee (EC) will review all deaths and classify the events as cardiovascular or non-cardiovascular (see Appendix J). Cardiovascular deaths will be further classified as sudden and non-

sudden based on a time criteria (see Appendix J). Adjudicated cause of death as well investigatorreported cause of death will be entered into the eCRF.

A subgroup of those patients that underwent an echocardiography at inclusion will be invited to participate in a similar echocardiography during follow-up. The criteria for invitation is that the participants should have been included in the LOOP study before January 2017 at one of the study centres Rigshospitalet, Bispebjerg Hospital or Roskilde Hospital, and that the first echocardiography should be between 2 and 6 years old at the time of follow-up echocardiography.

For endpoints, see section 10.2

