Hospital treatment will be valued with official hospital charges (diagnosis related group (DRG) charges) provided by the National Board of Health. Special attention to the relevance of using DRG charges will be considered. Services from private practising providers will be valued according to the prevailing fee schedules that are agreed upon between the providers and the regional health authorities. For the valuation of general practitioner services an annual amount will be added to take into account that general practitioners are paid by a combination of capitation and fee-for-service. Furthermore, patients' co-payments will be added. Data on the participants' use of prescription drugs will be collected from the Register of Medicinal Product Statistics. These drugs will be valued according to the pharmacy sales prices.

Information about the participants' use of services provided by the municipalities, e.g. community nurse visits, personal care and practical assistance at home, nursing home, respite care and rehabilitation, will be collected from the participants' municipality of residence. Unit costs of these

services will be estimated based on statistics on wage rates and databases that record the cost of providing home care, (e.g. The Free Choice Database (*Fritvalgsdatabasen*)), which is administered by the National Board of Social Services. All costs will be converted to a specific year price level using the consumer price index and other relevant price indices.

QALYs will be estimated with the use of the EQ-5D-5L instrument. Participants will fill in the EQ-5D-5L questionnaire at baseline (before operation) and every second year (mailed to control group). Each health state is converted to a social tariff (utility score) from a representative sample of the Danish population. This will be used to construct each participant's utility profile. A straight line relation between each of the observed utility scores will be assumed. The number of QALYs experienced by each participant will be calculated as the area under the participant's utility profile.

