Descriptive analyses will be used to describe the mean QALYs, resource use and costs per participant in both arms of the trial. Differences in QALYs, resource use and costs between the two groups after 24 months of the study will be based on the trial data. Confidence intervals of 95% for differences between the two groups will be computed based on bootstrap re-sampling with 5,000 replications of the trial data.

For the cost-effectiveness analyses, the incremental cost-effectiveness ration (ICER) will be estimated on the basis of the mean difference in costs relative to the mean difference in

QALYs. Uncertainty about the ICERs will be analysed using bootstrapping and presented in a cost-effectiveness plane. A cost-effectiveness acceptability curve will be generated to represent the probability that ILRs are cost-effective compared with usual treatment. Estimates of the costs per QALY gained from ILR will be compared to similar estimates of rehabilitation after stroke, AF management as well as other cost-effectiveness estimates in other treatment areas.

Study nurses will register all contacts between study subject and study nurse in the hospital files to be included in the cost evaluation.

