# 10.6.2.2 Secondary Endpoints:

See section 10.2.2.

For the time-to-event variables, analysis similar to the one employed for the primary endpoint will be used. The censoring mechanism will also be similar to the one used for the analysis of the primary endpoint. The secondary endpoints will be tested at a significance level of 0.05. Within the first two secondary endpoints the type 1 error rate associated with a multiplicity of comparisons will be controlled according to the Hochberg adjustment. The Quality of Life endpoint will be tested at the 5% significance level. Quality of Life score will be analysed as repeated measures analysis of covariance mixed effects model using baseline score as a covariate.

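### At 12 and 24 months quality-of-life forms are completed in hospital in the ILR arm and by mail in controls, so collection route is fully confounded with arm in the 24-month QALY difference and at two of the three QoL follow-up points

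*Protocol*

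**What the plan says.** - **ILR arm.** Section 7.2.1 (The main study): "Participants in the ILR group will be seen at in-hospital visits at 12, 24 and 36 months after ILR implantation". Of these visits it says: "At in-hospital visits, QoL and MoCA forms will be filled".
- **Control arm.** Same section: "Participants in the control group will be seen only at inclusion and after the 3 year follow-up". Between those two visits, "QoL forms will be sent by mail".
- **QoL time points.** The assessment list in the same section gives: "Assessment of QoL and cognitive function: At randomization, months 12, 24 and 36". Appendix A ticks QoL for controls at about 12, 24 and 36 months, but ECG and vital signs only at screening and about 36 months. This fits there being no control visit at 12 or 24 months.
- **Baseline.** Section 5.1 has the QoL questionnaires completed at the inclusion visit, in the same setting for both arms.
- **EQ-5D-5L.** Section 7.2.2, under Comments, schedules it at "baseline (before operation) and every second year (mailed to control group". Utilities are joined by straight lines and QALYs are the area underneath. Differences in QALYs and costs "after 24 months of the study will be based on the trial data".
- **QoL analysis.** Section 10.6.2.2 tests QoL at the 5% level: "Quality of Life score will be analysed as repeated measures analysis of covariance mixed effects model using baseline score as a covariate".

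The protocol neither equalises the route between arms nor plans a sensitivity analysis for it.

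**The concern.** At 12 and 24 months a participant's arm determines how the form is completed: at a hospital visit or at home by post. Setting can shift answers, and the route to missing data differs too. A control drops out of the QoL data by not returning a letter, and an ILR participant by missing a visit. A difference between arms at those times therefore combines any effect of screening with any effect of route.

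The analysis model cannot undo this. A mode term would be collinear with arm at 12 and 24 months. Baseline adjustment does not help because the split begins after baseline.

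Two results are exposed: the QoL test at 5%, and the 24-month QALY difference behind the cost-utility analysis. Cost-effectiveness is a secondary hypothesis in section 2.5.2, and section 1 (Expected results) intends the result to inform health policy.

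**Working it through.** The protocol gives no SD, effect size or power for QoL or QALYs, so there is no planned figure to reproduce.

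**Step 1: route by arm and time**

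| Time | ILR arm | Control arm | Same route? |
|---|---|---|---|
| Baseline | inclusion visit | inclusion visit | yes |
| 12 months | hospital visit | mail | no |
| 24 months | hospital visit | mail | no |
| 36 months | hospital visit | final visit (QoL there is inferred) | apparently yes |

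For controls at the final visit, section 7.2.1 names only the MoCA form. That QoL is also completed there follows from the month-36 entry in the assessment list and from Appendix A, but is not stated outright.

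**Step 2: bias in the 24-month QALY difference**

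Let m be a pure route effect on utility between arms at each split visit. Assumed range: 0 to 0.03, either sign. Apply the protocol's straight-line area rule with no true screening effect.

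- EQ-5D at 0 and 24 months (section 7.2.2): ½ × (0 + m) × 2 years = 1.0m.
- EQ-5D at 0, 12 and 24 months (if it follows the yearly list in 7.2.1): ½ × (0 + m) × 1 + ½ × (m + m) × 1 = 1.5m.

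| m | 1.0m | 1.5m |
|---|---|---|
| 0 | 0 | 0 |
| 0.01 | 0.010 | 0.015 |
| 0.02 | 0.020 | 0.030 |
| 0.03 | 0.030 | 0.045 |

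Extending a yearly profile to 36 months while keeping the 12- and 24-month values makes it worse: ½m + m + ½m = 2.0m.

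**Step 3: the QoL test**

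Section 10.6.2.2 names the model but not the contrast, so the result is conditional. Inputs: 1,500 versus 4,500 (synopsis), all responding, and a two-sided 5% test (sidedness is not stated for QoL). The assumed route shift is b, in SD units. The standard error is √(1/1500 + 1/4500) = 0.0298 SD. The chance of a significant difference with no screening effect is Φ(b/SE − 1.96) + Φ(−b/SE − 1.96).

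For an equal average of three visits, replace b by 2b/3. The single-visit SE is kept, which is conservative.

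| b (SD) | one split visit | equal average of 12, 24, 36 | month-36 contrast, same setting |
|---|---|---|---|
| 0 | 5.0% | 5.0% | 5.0% |
| 0.02 | 10.3% | 7.3% | 5.0% |
| 0.05 | 38.9% | 20.1% | 5.0% |
| 0.10 | 91.8% | 60.9% | 5.0% |

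The table shows how sensitive a comparison of this size is to a small artefact. It is not evidence that an artefact of any given size exists.

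**The case against.** **No mode effect is documented.** Section 7.2.2 says participants fill in the EQ-5D-5L themselves, and nothing describes an interview. The contrast may be only one of setting for a self-completed form, with a shift close to zero. This stands, so the assumed ranges start at zero.

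**A reader might infer that the QALY bias exceeds the real benefit several-fold.** The documents do not support that. The shift would have to be assumed non-zero, and a comparison with avoided strokes alone leaves out the reassurance, anxiety, mortality and bleeding effects that the protocol itself anticipates.

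**A reader might infer that the QoL test averages all follow-up visits.** Section 10.6.2.2 does not say so. A month-36 contrast would largely avoid the problem, and the choice may be made in an SAP that is not shown. The collection route, by contrast, is fixed in the protocol.

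**Missing data arise in both arms.** It is tempting to say that only controls lose forms, but ILR participants can miss visits. No rates are given. What stands is that the mechanism differs by arm.

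**The endpoints are minor and the trial is open-label.** QoL and QALYs are supplementary (section 10.2.4), and answers already reflect knowledge of allocation, which a common route would not remove. Both points are right and limit the weight of the finding. They do not justify adding a second, avoidable difference between arms.

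**Conclusion.** The confounding is real and follows from the protocol's own text: at 12 and 24 months, setting and route to non-response are determined by arm. It reaches every post-baseline utility in the 24-month QALY difference and two of the three follow-up points available to the QoL model, and baseline adjustment cannot remove it.

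Its size and direction cannot be derived from the document. For an assumed utility shift of 0 to 0.03, the QALY bias is 0 to 0.030 on the two-yearly EQ-5D schedule and 0 to 0.045 on a yearly one. The effect on the QoL test ranges from none to substantial, depending on the contrast chosen and on an unknown shift. The primary endpoint and the secondary endpoints listed in section 10.2.2 are not affected. The change is worth making because it is cheap, not because a large bias has been shown.

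**What to change.** **Collection.** Mail the same QoL/EQ-5D form to ILR participants for completion at home before the 12- and 24-month visits, as controls do. The cost is postage for about 1,500 forms per mailing and possibly some extra non-response in the ILR arm.

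**Data already collected: QoL.** First confirm that controls complete QoL at the final visit. Then name the 36-month contrast in section 10.6.2.2 as the formal 5% test and report the 12- and 24-month contrasts as descriptive. The cost is a wording change and fewer visits contributing to the formal test.

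**Data already collected: QALYs.** Report the 24-month difference with a sensitivity analysis over a range of route shifts, including zero and both signs, and one for non-response that differs by arm. Do not lengthen the window to 36 months while keeping the 12- and 24-month values, since that raises the bias to 2.0m.

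**Schedule.** Reconcile the two-yearly EQ-5D interval in section 7.2.2 with the yearly QoL list in section 7.2.1. Until that is done it is unclear whether 12- and 36-month utilities exist at all.
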